5.4.5.4. Echocardiography

Standard 2D/Doppler echocardiography is performed at a subset of centers. Echocardiography assessments in AC-058B202 are only conducted in subjects who were assessed during the core study.

All echocardiography results are stored in SDTM201.MO/SDTM202.MO together with nominal visit and timepoint information. The two MO datasets are concatenated for the purposes of derivations and analysis. The corresponding coded preferred terms are stored in SDTM201.SUPPMO/SDTM202.SUPPMO where QNAM is MODECOD.

Echocardiography parameters

The following quantitative echocardiography parameters are evaluated by the central reader (Methodist): left ventricular ejection fraction (LVEF) diameters (%), left ventricular (LV) diastolic dimension (cm), LV mean thickness (cm), LV posterior wall (LVPW) diastolic thickness (cm), IVS (cm), left atrial single plane area (cm²), left atrial single plane volume (mL), aortic root diastolic diameter (cm).

The ponesimod baseline value (as described in Section 5.1.2) is flagged in the AdaM dataset.

Absolute and percentage change from ponesimod baseline are derived for all post-baseline assessments.

All nominal visits are re-windowed based on the visit schedule in Section 5.1.7.

Echocardiography findings

Echocardiography findings are evaluated centrally and coded using MedDRA version 26. Treatment-emergent findings are flagged in the AdaM dataset. Treatment-emergent findings are

```
CONFIDENTIAL – FOIA Exemptions Apply in U.S.
```

any findings that were reported after first dose of ponesimod and within 15 days of last dose of ponesimod, and that either were not present at any assessment prior to first dose of ponesimod, or worsened from an assessment observed prior to first dose of ponesimod (per the rules described below).

Echocardiography findings include the following:

- All coded findings that were not present at any assessment prior to first dose of ponesimod.
- Cardiac Valves Regurgitation findings defined as:

No regurgitation finding at any assessment prior to first dose of ponesimod and present as 'Trace', 'Mild', 'Moderate' or Severe' at any assessment after first dose of ponesimod.

Regurgitation finding present at one or more assessments prior to first dose of ponesimod and worsening after first dose of ponesimod, e.g., ticked 'Trace' at the screening and 'Mild' at any post-baseline visit.

The following summaries are produced for quantitative echocardiography parameters (LVEF diameters, LV diastolic dimension, LV mean thickness, LVPW diastolic thickness, IVS, left atrial single plane area, left atrial single plane volume, aortic root diastolic diameter) by treatment group:

- Summary of absolute values for echocardiography parameters: descriptive statistics by analysis visit (AP3 on the echocardiography analysis set);
- Summary of absolute values and absolute change from ponesimod baseline values for echocardiography parameters: descriptive statistics by analysis visit (AP3 on the echocardiography analysis set);
- Summary of percent change from ponesimod baseline values for echocardiography parameters: descriptive statistics by analysis visit (AP3 on the echocardiography analysis set);

The following summaries are produced for echocardiography findings by treatment group:

- Incidence of new treatment-emergent MedDRA (i.e. not present at ponesimod baseline) coded echocardiography findings [as defined above], by preferred term: frequency counts and percentages (AP3 on the echocardiography analysis set);
- Treatment-emergent Cardiac Valves Regurgitation findings are summarized as follows (examples) percentages (AP3 on the echocardiography analysis set):
 - Aortic Valve Regurgitation: Mild;
 - Aortic Valve Regurgitation: Moderate;
 - Mitral Valve Regurgitation: Trace;
 - Mitral Valve Regurgitation: Moderate.

Each abnormal finding is only counted once. The worst outcome reported post-baseline is considered. Tables present the number and percentage of subjects having any new abnormality and having each specific new abnormality.

A full listing of all echocardiography data is provided based on the echocardiography analysis set.

Note that the core study B201 used a different dictionary (PSID) than that being used for the current study for Echocardiography findings. As certain terms may differ between the two dictionaries, and since a finding is defined relative to the first dose of ponesimod, this has an impact on what is identified as an Echocardiography finding. A footnote will be added to the echocardiography outputs to indicate that not all identified findings may indeed be findings (i.e. appearing for the first time).

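### New coded echocardiography findings are derived across two dictionaries, so a persisting finding can be tabulated as new; the planned footnote discloses this but does not correct the table

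*SAP*

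**What the plan says.** SAP 5.4.5.4 combines the two studies' echocardiography records: "The two MO datasets are concatenated for the purposes of derivations and analysis". Coded terms come from each study's own supplemental dataset. A coded finding counts as treatment-emergent if it was reported after the first ponesimod dose, and within 15 days of the last, and was not present at any assessment before the first dose. Valve regurgitation has a separate rule based on grade. On the resulting output the section says: "Tables present the number and percentage of subjects having any new abnormality and having each specific new abnormality".

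The section then adds a caution. The "core study B201 used a different dictionary (PSID) than that being used for the current study for Echocardiography findings". It continues: "As certain terms may differ between the two dictionaries, and since a finding is defined relative to the first dose of ponesimod", there is an effect on what gets identified as a finding. Two outputs bear on this. One is a footnote that "will be added to the echocardiography outputs to indicate that not all identified findings may indeed be findings (i.e. appearing for the first time"). The other is the listing: "A full listing of all echocardiography data is provided based on the echocardiography analysis set". No recoding of core terms, dictionary map, review of flagged findings or sensitivity table is described.

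Elsewhere, SAP 5.1.7 says echocardiography findings are coded in MedDRA 26.0 and makes no exception for core data. The findings paragraph of 5.4.5.4 says the same.

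**The concern.** The word new depends on matching a term seen after the first dose with the terms seen before it. If the two sides use different vocabularies, a failed match may reflect wording and not a change in the heart. The SAP recognises this and still tabulates the unmatched terms as new abnormalities.

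Protocol 5.6 plans a summary of treatment-emergent echocardiography abnormalities by treatment group. The extension has no control arm, so readers will look mainly at absolute incidence, which is what a term mismatch distorts. A raised count for one term could be an artefact, and the footnote, as described, will not tell the reader which rows are affected or by how many subjects.

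**Working it through.** There is no planned figure to reproduce. The documents do not give the number of subjects with echocardiography, how often coded findings were present before dosing, or the share of terms that differ. The check is therefore a trace through the text.

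**Where the pre-dose reads come from.** On eligibility, SAP 5.4.5.4 says: "Echocardiography assessments in AC-058B202 are only conducted in subjects who were assessed during the core study". Protocol 3.12.2.5 places the first scheduled extension echocardiogram at Week 12 (Visit E6), after ponesimod has started for everyone. Protocol Table 1 shows an echocardiogram at the core Week 24 visit and none at Visit E1. All scheduled reads before first ponesimod are therefore core reads, both for subjects randomized to ponesimod in the core study and for those who switched from placebo.

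**Which comparisons cross dictionaries.** Any finding at an extension visit is compared with core terms. A finding at a core visit after dosing, in a subject randomized to ponesimod in the core study, is compared within one dictionary.

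**What the rule does.** Suppose core terms were left in the PSID vocabulary.

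| Before first ponesimod (core term) | Extension (MedDRA term) | Result under the rule | True status |
|---|---|---|---|
| Abnormality present, same wording in both | Still present | Not new | Not new |
| Abnormality present, wording differs | Still present | New | Not new |
| Broad core term present | Different abnormality coded to that same term | Not new | New |
| Nothing present | Abnormality present | New | New |

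The second line is the over-count that the SAP's footnote describes. The third is a possible under-count that the SAP does not mention. The line-two error enters the row for any new abnormality when the subject has no genuine new finding, and it also enters the row for the specific term.

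**Whether core terms were recoded.** SAP 5.1.7 and the findings paragraph of 5.4.5.4 can be read to say that all echocardiography findings, core included, are in MedDRA 26. The later note in 5.4.5.4 says the core used PSID and that this changes the result. Both cannot hold for the core data as analysed. If core terms were recoded, the second line of the table does not arise from the dictionary, and the note and footnote should go. If they were not, the MedDRA statements are wrong for core data and the misclassification is live. The note is specific to this analysis, and coded terms are drawn from each study's own dataset; both favour the second reading.

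**A further change over time.** The clarifications table in SAP 6.2.3 records, against Section 5.4.5.4, that the criteria for echocardiogram abnormality changed after the 2019 interim analysis. SAP 5.4.5.3 makes a near-identical statement about ECG findings. Section 5.4.5.4 does not say how such a change is handled when new is derived, so mapping the dictionaries may not by itself make early and late reads comparable.

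**The case against.** The strongest reply is that the SAP has already dealt with this openly. It names the cause and the consequence, attaches a footnote, and lists all the data, so a reader can check individual subjects. Placebo-period visits are retained in the analysis datasets (SAP 5.1.9), so the pre-dose records are available. The analysis is exploratory and comes from an ancillary study at selected centers. Ejection fraction, a named protocol endpoint, does not depend on any dictionary. Over-counting is also in keeping with the SAP's habit of resolving doubt conservatively, as with missing intensity or causality of adverse events.

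Much of this stands, and it limits how serious the point is. It does not make the percentages right. The SAP plans no subject-level check from the listing, and a general footnote leaves every row equally doubtful.

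Three stronger inferences are tempting and are not supported. A reader might infer that the row for any new abnormality is certainly biased upward, by a calculable number of points. The SAP says only that terms may differ, term mismatch can also hide a new finding, and the inputs for a size are absent. A reader might infer that one abnormality must be split between a core-term row and a MedDRA row. That holds only if core terms were not recoded and both vocabularies are tabulated, which the SAP leaves unclear. A reader might also infer that dose comparisons are undermined. The cross-dictionary comparison occurs in all three dose groups, and nothing in the documents shows that it affects them differently.

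**Conclusion.** The point holds as a should-fix on one safety table. As written, the derivation can report persisting abnormalities as new, and the planned footnote and listing disclose this without correcting the counts. The size is unknown and the net direction is not established; over-counting is what the SAP itself anticipates. The conclusion assumes that core terms reach the analysis in the PSID vocabulary, which is the more natural reading of SAP 5.4.5.4 but conflicts with SAP 5.1.7.

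The scope is narrow: coded echocardiography findings only. Ejection fraction and the dimension summaries are untouched, and graded regurgitation, which has its own presence-or-worsening rule, is probably less exposed.

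**What to change.** 1. Before deriving treatment-emergence, code the distinct core and extension echocardiography terms in one MedDRA version, or apply a documented PSID-to-MedDRA map, and derive and tabulate on the harmonized terms. The SAP already codes pooled adverse events to a single version (Section 5.4.3).
2. For terms that cannot be mapped, check each apparent new finding against that subject's pre-dose echocardiography record. Show the incidence with and without those terms, and name them in the footnote.
3. Reconcile SAP 5.1.7 and the findings paragraph of 5.4.5.4 with the PSID note. If core data were in fact recoded, remove the note and the footnote.
4. State whether the change in abnormality criteria recorded in SAP 6.2.3 applies to echocardiography and, if so, how it is handled when new is derived.

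The cost should be a short mapping list, since only selected centers contribute, plus a rerun of the coded-findings table and some coding judgement. No new data collection is needed. The documents do not say whether the core verbatim terms are available; if they are not, more terms will need the record check in step 2.

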5.4.5.5. Pulmonary Function Tests

All pulmonary function test (PFT) results are stored in SDTM201.RE/SDTM202.RE together with nominal visit and timepoint information. The two RE datasets are concatenated for the purposes of derivations and analysis.

Note that, as of the implementation of Global Protocol version 12, the bronchodilator assessment is no longer required.

PFTs are performed pre-dose at the following assessments, and the parameters forced expiratory volume in 1 second (FEV_1 ; L) and forced vital capacity (FVC; L) are collected at the following visits in the extension study:

- TP1: at Visits E2 and E3 (Days 8 and 15), Visits E4 to E7, E9, E11 and E13;
- TP2 and TP3: at every other visit (from P1 to EOT3);
- Follow-up: at Visits E1 and E2 or FU1, FU2 and FU3 (EOS3).

At selected visits a bronchodilator assessment is performed (required yearly from Visit P1 during TP2 and recommended yearly during TP3). At such visits, two pre-dose PFT assessments are performed:

- One PFT assessment prior to administration of the bronchodilator ("Pre-bronchodilator");
- A second PFT assessment 30 minutes (± 15 minutes) after administration of the bronchodilator ("Post-bronchodilator").

The following additional PFT parameters variables are derived in the AdaM dataset:

• **FEV**₁/**FVC**(%)

The ratio (in %) between FEV_1 and FVC is calculated as:

$$FEV_1/FVC (\%) = \frac{FEV_1}{FVC} * 100$$

• Predicted normal values for FEV₁ and FVC

Predicted normal values for FEV_1 and FVC are calculated based on the following formulas [Quanjer 1993], where height and race are used as recorded at screening of the core study. Age is re-calculated at each assessment, by adding the time since the assessment where age was originally recorded to the original age value.

Predicted normal value for FEV₁ (L); H: standing height (m); A: age (years):

Sex	Equation
Male	4.30 H - 0.029 A* - 2.49
Female	3.95 H - 0.025 A* - 2.60

CONFIDENTIAL – FOIA Exemptions Apply in U.S.

Status: Approved, Date: 20 September 2023

Sex	Equation
Male	5.76 H - 0.026 A* - 4.34
Female	4.43 H – 0.026 A* – 2.89

Predicted normal value for FVC (L); H: standing height (m); A: age (yr):

*If age is between 18 and 25 (limits included), substitute with 25.

For patients of ethnic groups (race) other than 'Caucasian/White' the above predicted normal value must be multiplied by a conversion factor of 0.9 [Quanjer 1993].

• Percent of the predicted normal values for FEV1 and FVC

Percent of the corresponding predicted normal value is calculated for FEV_1 and FVC as follows:

 $\circ~$ Percent of the predicted value (%) = [measured value] $\times~100$ / [predicted normal value].

For all collected and derived PFT parameters, the following variables are derived:

The ponesimod baseline values (as described in Section 5.1.2) are flagged in the AdaM dataset. At visits where both pre- and post- bronchodilator assessments are taken, only the pre-bronchodilator assessment is considered for baseline.

Absolute and percentage change from ponesimod baseline are derived for all post-baseline assessments (except post-bronchodilator assessments).

At assessments where the bronchodilator is administered, absolute and percentage change from pre-bronchodilator to post-bronchodilator value is derived.

All nominal visits are re-windowed based on the visit schedule in Section 5.1.7.

Nominal assessments meeting the following conditions are flagged in the AdaM dataset:

Outliers:

- Percent change from ponesimod baseline in FEV₁: < -20 %, < -30%;
- Percent change from ponesimod baseline in FVC: < -20 %, < -30%;
- Absolute change from ponesimod baseline in % predicted FEV_1 : < -20 %, < -30%;
- Absolute change from ponesimod baseline in % predicted FVC: < -20 %, < -30%;
- $FEV_1/FVC < 70\%$.

Positive test for bronchodilator:

- Absolute change from pre- to post-bronchodilator in FEV₁ > 200 mL and percent change from pre to post-bronchodilator in FEV₁ > 12 %;
- Absolute change from pre- to post-bronchodilator in FVC > 200 mL and percent change from pre to post-bronchodilator in FVC > 12 %.

By Treatment group

The following summaries are produced for PFT parameters (FEV₁, FVC, FEV₁/FVC, %pred FEV₁, %pred FVC) by treatment group (post-bronchodilator assessments are not included):

- Summary of absolute values for PFT parameters: descriptive statistics by analysis visit (AP3 on the PAS) by treatment group;
- Summary of absolute change from ponesimod baseline values for PFT parameters: descriptive statistics by analysis visit (AP3 on the PAS) by treatment group;
- Summary of percent change from ponesimod baseline values for PFT parameters: descriptive statistics by analysis visit (AP3 on the PAS) by treatment group;
- Incidence of treatment-emergent PFT outliers [as defined above frequency counts, percentages, where percentages are based on the number of subjects at risk, i.e. number of subjects with at least 1 post-baseline value in that category during the analysis period (AP3 on the PAS) by treatment group.

The following plot is produced:

A plot of %pred FEV₁ values over time (including FU visits), by analysis visit (AP3 on the PAS) by treatment group;

By Post-Treatment DMT Subgroup

The following summaries are produced for PFT parameters by Post-Treatment DMT subgroup, as defined in Section 5.5.6 (pooling across all treatment groups):

- Summary of absolute values at ponesimod baseline, at last on-treatment and at each followup visit (FU7, FU30, FU90 and Last FU) for PFT parameters: descriptive statistics by analysis visit (AP3 on the PAS), by Post-Treatment DMT subgroups ((Any DMT, including ponesimod), No DMT).
- Summary of absolute change from ponesimod baseline to last on-treatment and each follow-up visit (FU7, FU30, FU90 and Last FU) for PFT parameters: descriptive statistics by analysis visit (AP3 on the PAS), by Post-Treatment DMT subgroup ((Any DMT, including ponesimod), No DMT).
- Summary of percent change from ponesimod baseline to last on-treatment and each followup visit (FU7, FU30, FU90 and Last FU) for PFT parameters: descriptive statistics by analysis visit (AP3 on the PAS), by Post-Treatment DMT subgroup ((Any DMT, including ponesimod), No DMT).

The following plots are produced:

- A plot of ponesimod baseline, last-on-treatment and follow-up values for %pred FEV₁, by analysis visit (AP3 on the PAS), by Post-Treatment DMT subgroup ((Any DMT, including ponesimod), No DMT).
- A plot of absolute change from ponesimod baseline to last-on-treatment and follow-up values for %pred FEV₁, by analysis visit (AP3 on the PAS), by Post-Treatment DMT subgroup ((Any DMT, including ponesimod), No DMT).

By Total Exposure Duration Subgroup:

The following summaries are produced for PFT parameters by the Total Exposure Duration subgroup, as defined in Section 5.5.6 (pooling all treatment groups).

- Summary of absolute values at ponesimod baseline, at last on-treatment and at each followup visit (FU7, FU30, FU90 and Last FU) for PFT parameters: descriptive statistics by analysis visit (AP3 on the PAS), by the Total Exposure Duration subgroup.
- Summary of absolute change from ponesimod baseline to last on-treatment and each follow-up visit (FU7, FU30, FU90 and Last FU) for PFT parameters: descriptive statistics by analysis visit (AP3 on the PAS), by the Total Exposure Duration subgroup.
- Summary of percent change from ponesimod baseline to last on-treatment and each followup visit (FU7, FU30, FU90 and Last FU) for PFT parameters: descriptive statistics by analysis visit (AP3 on the PAS), by the Total Exposure Duration subgroup.

The following plots are produced:

- A plot of ponesimod baseline, last-on-treatment and follow-up values for %pred FEV₁, by analysis visit (AP3 on the PAS), by the Total Exposure Duration subgroup.
- A plot of absolute change from ponesimod baseline to last-on-treatment and follow up values for %pred FEV₁, by analysis visit (AP3 on the PAS), by the Total Exposure Duration subgroup.

The following summaries are produced for PFT parameters (FEV₁, FVC, FEV₁/FVC, %pred FEV₁, %pred FVC) for pre-/post-bronchodilator assessments by treatment group:

- Summary of absolute values for PFT parameters at pre- and post-bronchodilator assessments: descriptive statistics by analysis visit (AP3 on the PAS);
- Summary of absolute change from pre- to post-bronchodilator assessment for PFT parameters: descriptive statistics by analysis visit (AP3 on the PAS);
- Summary of percent change from pre- to post-bronchodilator assessment values for PFT parameters: descriptive statistics by analysis visit (AP3 on the PAS);
- Incidence of positive test for bronchodilator [as defined above]: frequency counts, percentages, where percentages are based on the number of subjects at risk, i.e., number of subjects with at least 1 bronchodilator administration with pre and post PFT performed during the analysis period (AP3 on the PAS).

The following plots are produced for pre-/post-bronchodilator assessments of PFT parameters by treatment group:

• A plot of all pre/post-bronchodilator %FEV₁ values over time, by analysis visit (AP3 on the PAS).

A listing of outliers and positive tests for bronchodilators for PFT data is provided for AP3 on the PAS.

